3.4. Selection of Study Population

3.4.1. Planned Sample Size

Up to 66 healthy volunteers.

3.4.2. Inclusion criteria

1. Signing of the Informed Consent Form;
2. Male sex;
3. Age of 18 to 45 years, inclusive;
4. BMI within normal limits (18.5–24.9 kg/m²);
5. Healthy patients, which is proved by their medical history, physical examination and laboratory findings:
 - No clinically significant abnormalities of circulatory, respiratory, nervous, hematopoietic, endocrine and digestive systems, liver and kidneys in the past medical history and at screening;
 - No history of cardiovascular disorders or thyroid disorders;
 - No history of hematologic disorders, including but not limited to any type of anemia, myelodysplastic syndrome, blood cancers, hemolytic syndrome, hemoglobinopathies, coagulopathies;
 - CBC results within normal limits, including:
 - Hemoglobin within 132–173 g/L;
 - Hematocrit (based on CBC results) within 39–49%;
 - Platelet count within 150–400*10⁹/L;
 - Absolute reticulocyte count within 30.4–93.5 * 10⁹/L;
 - Blood biochemistry and urinalysis results within normal limits;
 - Serum ferritin within 20–250 µg/L;
 - Serum endogenous erythropoietin within 4.3–29.0 MIU/mL;
 - Hemodynamic parameters within normal limits: systolic blood pressure within 100–139 mmHg; diastolic blood pressure within 60–90 mmHg; heart rate within 50–90 bpm;
 - No history of chronic infections (tuberculosis) or chronic inflammation;
 - No hepatitis B or C, HIV, or syphilis;
 - No acute infections within 4 weeks prior to inclusion in the study;
 - No psychiatric disorders and other conditions (including depression) that can interfere with the volunteer's ability to follow the study protocol;

- Well-being (in the volunteer's opinion) within 30 days prior to inclusion in the study;
- 6. No history of or current (at baseline) alcohol or drug abuse;
- 7. Ability of the volunteer, in the investigator's opinion, to follow the study protocol procedures;
- 8. Willingness of volunteers and their sexual partners with preserved reproductive potential to use reliable contraception within 2 weeks before inclusion in the study and up to 7 weeks after the injection of the test product. This criterion is not applicable to subjects who underwent surgical sterilization. Reliable methods of contraception include one barrier method in combination with one of the following methods: spermicides, intrauterine device/oral contraceptives (for sexual partners).
- 9. Willingness of volunteers to avoid alcohol intake within 24 hours before and 8 days after each injection of the test drug;

3.4.3. Exclusion criteria

1. History of treatment with erythropoietins or any other ESAs;
2. Acute bleeding, blood/plasma donation or blood transfusion within 2 months before inclusion in the study;
3. History of chronic bleeding;
4. Standard laboratory and instrumental findings outside normal limits at screening;
5. History of allergies (anaphylactic shock or multiple drug allergy syndrome);
6. Known allergy or intolerance to any components of the investigational product;
7. Major surgery within 30 days prior to screening, or surgery being scheduled for any time during the study;
8. Impossibility to install a venous catheter for blood sampling (e.g. because of skin disorders at the sites of venipuncture);
9. Diseases or other conditions that can interfere with the pharmacokinetics of the investigational drug (e.g. chronic liver, kidney, blood, circulatory system, lung or neuroendocrine diseases, including diabetes mellitus and others);
10. History of fever of 40 °C or more;
11. History of elevated hepatic transaminases (above 2.5xULN);

12. Episodes of thrombosis and/or thromboembolia in past medical history (myocardial infarction, stroke, transient ischemic attacks, deep vein thrombosis, pulmonary embolism within 6 months prior to inclusion in the study) as well as an increased risk of deep vein thrombosis;
13. History of epileptic attacks or seizures;
14. History or current (at screening) depression, suicidal thoughts/ attempts;
15. Regular oral or parenteral use of any medications including over-the-counter drugs, vitamins and nutritional additives within 2 weeks before a scheduled injection of the test drug;
16. Use of drugs, including OTC products, that significantly affect the hemodynamics, hepatic function, etc. (barbiturates, omeprazole, cimetidine, etc.) within 30 days before a scheduled injection of the test drug;
17. Vaccination within 4 weeks before a scheduled injection of the test drug;
18. Smoking more than 10 cigarettes per day;
19. Consumption of more than 10 portions of alcohol per week (one portion equals to 0.5 L of beer, 200 mL of wine or 50 mL of ethanol) or a history of alcohol, drug or medication abuse;
20. Participation in other clinical studies within 1 month before screening or simultaneous participation in another clinical study;
21. Previous participation in this study.

4. EVALUATION CRITERIA

4.1 Endpoints to Evaluate Single-Dose Pharmacokinetics

Primary endpoint

- $AUC_{0-1176\text{ h}}$ (area under the concentration vs. time curve from the moment of injection to 1176 h [Day 50 of follow-up]) and $AUC_{0-\infty}$ (to infinity).

Secondary endpoints

- C_{\max} (maximum serum concentration),
- T_{\max} (time to C_{\max}),
- $T^{1/2}$ (half-life),

- k_{el} (elimination constant),
- CL (total clearance).

4.2. Pharmacodynamics Endpoints

Primary endpoint

- AUEC0-1176 h (total area under the effect vs. time curve from the moment of injection to 1176 h [Day 50 of follow-up]) based on the change in the absolute reticulocyte count after a single-dose injection of the drug product.
- AC-Emax (absolute maximum increase in the test parameter vs. baseline) based on the change in the absolute reticulocyte count in the blood after a single-dose injection of the drug product.

Secondary endpoints:

- AUEC0-1176 h (total area under the effect vs. time curve from the moment of injection to 1176 h [Day 50 of follow-up]) based on the change in the Hb level in the blood after a single-dose injection of the drug product.
- AC-Emax (absolute maximum increase in the test parameter vs. baseline) based on the change in the Hb level in the blood after a single-dose injection of the drug product.

4.3. Endpoint for Pain Assessment

- The average VAS score evaluating the pain during the injection.

4.4. Safety assessment

- Total SAEs.
- Total AEs.
- Incidence of administration site reactions.
- Incidence of Grade 3-4 AEs and SAEs.
- Frequency of early withdrawals due to AEs and SAEs.

4.5. Immunogenicity Endpoints

- Incidence of BAbs to the drug product on Day 50 from the moment of a single-dose injection of the drug.

5. THE PLANNED ANALYSIS

The study report will be made after the study completion (after all included patients will finish the study).

6. SAMPLE SIZE CALCULATION

The sample size for the study was calculated based on the “3+3” design used in the study of doses and additional test parameters:

Cohort	Dose, µg/kg	Number of volunteers to be enrolled (obligatory)	Number of volunteers who can be enrolled if DLT signs develop
01	0.05	3	3
02	0.15	3	3
03	0.40	3	3
04	1.05	3	3
05	1.70	3	3
06	2.75	3	3
07	4.45	3	3

To assess the PK and PD of the closest analogues of BCD-131, 6 more volunteers will be included in the study to receive Mircera® and 6 more volunteers will be enrolled to receive Aranesp®.

To assess the PK and PD of BCD-131 given as a subcutaneous or intravenous injection at a dose established at stage I of the study, 6 more volunteers will be included in the study to receive BCD-131 as an intravenous injection and 6 more volunteers will be enrolled to receive BCD-131 as a subcutaneous injection.

7. STATISTICAL ANALYSIS OF POPULATION

Pharmacokinetics analysis

The pharmacokinetics (PK) analysis will include data of all volunteers who have received one dose of BCD-131 or reference drugs. If a subject has had more than two PK serum samples missed / lost / spoilt and skipped blood sampling time points more than twice, his/her data will not be included in the PK analysis.

Pharmacodynamics analysis

The pharmacodynamics (PD) analysis will include data of all volunteers who have received one dose of BCD-131 or reference drugs. If a subject has had more than two PK serum samples missed / lost / spoilt and skipped blood sampling time points more than twice, his/her data will not be included in the PD analysis.

Safety analysis

The safety analysis will include all patients who have received one dose of the test/reference drug.

Immunogenicity analysis

The immunogenicity analysis will include data of all volunteers who have received one dose of BCD-131 or reference drugs. If a subject has had serum samples taken on Day 1 and Day 50 missed / lost / spoilt, his/her data will not be included in the immunogenicity analysis.

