**PK analysis**

The PK analysis will include data of all volunteers who have received one dose of BCD-131 or reference drugs. If a subject has had more than two PK serum samples missed / lost / spoilt and skipped blood sampling time points more than twice, his/her data will not be included in the PK analysis.

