**PD analysis**

The PD analysis will include data of all volunteers who have received one dose of BCD-131 or reference drugs. If a subject has had more than two PK serum samples missed / lost / spoilt and skipped blood

	
sampling time points more than twice, his/her data will not be included in the PD analysis.
 
Safety analysis
 
The safety analysis will include all patients who have received one dose of the test/reference drug.
 
Immunogenicity analysis
 
The immunogenicity analysis will include data of all volunteers who have received one dose of BCD-131 or reference drugs. If a subject has had serum samples taken on Day 1 and Day 50 missed / lost / spoilt, his/her data will not be included in the immunogenicity analysis.

--	--

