If during 14 days after the injection of BCD-131 the subjects do not develop any treatment-emergent Grade 3-4 AEs (DLT), the next cohort consisting of three volunteers will be included in the study to receive an escalated dose of BCD-131 (Cohort 03, Cohort 04, Cohort 05 etc.).

If during 14 days after the injection of BCD-131 only one volunteer (of three) develops a treatment-emergent Grade 3-4 AE (DLT), three more healthy volunteers will be included in this cohort to receive BCD-131.

If two subjects develop treatment-emergent Grade 3-4 AEs (DLT), the dose of BCD-131 which resulted in these events is considered to be the maximum tolerated dose (MTD). No further dose escalating is performed.

Thus, the dose-limiting toxicity is assessed as close as possible to the time of drug administration during the first 14 days after the injection. However, follow-up of volunteers does not stop; it will continue up to Day 50 from the moment of injection and include the monitoring of volunteers' health as well as safety and PK parameters of BCD-131.

Evaluation of pharmacokinetics, pharmacodynamics and safety of subcutaneous therapeutic doses of Mircera® and Aranesp®

Simultaneously with the evaluation of pharmacokinetics, pharmacodynamics and safety of ascending doses of BCD-131, the investigators will evaluate the pharmacokinetics, pharmacodynamics and safety of subcutaneous therapeutic doses of Mircera® and Aranesp®. For this purpose, 12 more volunteers will be included in the study.

After having been randomized in a 1:1 ratio, the volunteers will be assigned to 2 groups. Six volunteers in Group 1 will receive a single subcutaneous injection of Mircera® at a dose of 1.20 µg/kg (Day 1). Six volunteers in Group 2 will receive a single subcutaneous injection of Aranesp® at a dose of 0.45 µg/kg (Day 1).

After the last volunteer enrolled in stage I of the study has completed all the procedures specified in the Study Protocol, an interim analysis of the data obtained will be performed. Based on the comparison of pharmacokinetics, pharmacodynamics and safety of different doses of the test drug and active comparators, the investigators will establish a dose of BCD-131 which ensures PD effects similar to those of the closest analogues (Mircera®, Aranesp®) given as subcutaneous injections at therapeutic doses. The established dose of BCD-131 will be used at stage II of the study.

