8.2. Description of the Statistical Methods to be Employed

Quantitative Data

The following quantitative data will be analyzed in the study:

Pharmacokinetics:

- Plasma concentration of drug,
- Area under plasma concentration curve,
- Time (e.g., maximum plasma concentration time, half-life)

- Elimination parameters (e.g. clearance, terminal rate constant)

Pain Assessment:

- VAS score

Safety:

- CBC results,
- Blood chemistry results,
- Vital signs;
- ECG findings,
- Urea analysis results,
- Skin disorders size at the sites of venipuncture,
- Skin disorders lifetime at the sites of venipuncture.

Pharmacodynamics:

- absolute reticulocyte count.
- Hb level.
- Area under effect curve «absolute reticulocyte count — time».
- Area under effect curve «Hb level — time».
- Time (e.g. the time of the maximum increase of absolute reticulocyte count vs. baseline).

The statistical analysis will include two-tailed hypothesis testing; the chosen significance level is 0.05.

Quantitative variables will be tested for normality using the Shapiro-Wilk test.

Normally distributed quantitative variables will be tested using the two-sample Student's t-test, Welch's t-test, and ANOVA.

Non-normally distributed quantitative variables will be tested using the Mann-Whitney U-test, the Wilcoxon test, the Kruskal-Wallis test, and the Friedman test.

Normally distributed quantitative data will be described using the following descriptive statistics: mean, SD, CV, min, and max. Non-normally distributed quantitative data will be described using the following descriptive statistics: median, quartiles, CV, min, and max.

Categorical Data

The following categorical data will be analyzed in the study:

Safety:

- Skin disorders sort at the sites of venipuncture.
- Rate and severity grades of AEs/SAEs,
- Rate of Grade 3-4 AEs,
- Frequency of local reactions (total and by skin disorder type).
- Frequency of early study termination cases by AEs/SAEs.

Categorical data will be processed using frequency tables, contingency tables, the Fisher's exact test, the test of equal frequencies, Pearson's χ^2 test, and the Cochran-Mantel-Haenszel test. Percentages or proportions will be used to describe categorical data.

The Benjamini-Yekutieli correction for multiple testing will be used.

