$t_p \in \{ 0; 24; 48; 72; 96; 120; 168; 216; 288; 336; 504; 672; 840; 1008; 1176 \}; p=1, \dots, 15$

2. **AUEC₍₀₋₁₁₇₆₎** - (area under effect curve from the moment of injection to 1176 h [Day 50 of follow-up]) based on the change in the Hb level in the blood after a single-dose injection of the drug product:

$$AUEC_{(0-1176)} = \sum_{p=2}^{15} \frac{(C_p + C_{p-1}) * (t_p - t_{p-1})}{2},$$

where C_p the Hb level at the moment t_p (hours);

$t_p \in \{ 0; 24; 48; 72; 96; 120; 168; 216; 288; 336; 504; 672; 840; 1008; 1176 \}; p=1, \dots, 15$

3. AC-E_{max} (absolute maximum increase in the test parameter vs. baseline) based on the change in the absolute reticulocyte count in the blood after a single-dose injection of the drug product.
4. AC-E_{max} (absolute maximum increase in the test parameter vs. baseline) based on the change in the Hb level in the blood after a single-dose injection of the drug product.

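### The PD analysis set is decided by lost PK samples rather than by reticulocyte and Hb values, and the immunogenicity set rule does not match its Day-50 endpoint

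*SAP*

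**What the plan says.** **PD set.** SAP section 7 gives one exclusion condition for the PK set, "more than two PK serum samples missed / lost / spoilt and skipped blood sampling time points more than twice", and repeats it for the PD set, ending "skipped blood sampling time points more than twice, his/her data will not be included in the PD analysis". The protocol synopsis does the same. Its PK paragraph counts "more than two PK serum samples missed / lost / spoilt", and its PD paragraph repeats that condition and closes with "sampling time points more than twice, his/her data will not be included in the PD analysis". The SAP therefore follows the protocol here.

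**PD endpoints.** SAP 4.2 makes AUEC and AC-Emax for reticulocytes primary, the latter defined as "AC-Emax (absolute maximum increase in the test parameter vs. baseline) based on the change in the absolute reticulocyte count in the blood". The same two measures for Hb are secondary. SAP 8.4 computes AUEC over 15 times, in hours: "0; 24; 48; 72; 96; 120; 168; 216; 288; 336; 504; 672; 840; 1008; 1176".

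**Use of the PD results.** After Stage I, according to SAP 3.1, "the investigators will establish a dose of BCD-131 which ensures PD effects similar to those of the closest analogues". SAP section 6 plans three volunteers per BCD-131 cohort, with three more if dose-limiting toxicity appears, and six per comparator group.

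**Immunogenicity set.** SAP section 7 and the protocol synopsis exclude a volunteer whose Day 1 and Day 50 serum samples are both unavailable, if the conjunction is read literally. The only immunogenicity endpoint, in SAP 4.5, is the incidence of binding antibodies on Day 50.

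**The concern.** An analysis set should be defined by the data that its endpoint needs. The PD rule counts a different specimen, so it can err in two directions: it can discard complete PD data because PK tubes were lost, and it places no limit on lost blood counts when the PK tubes are intact. In cohorts of three, set membership of one person carries real weight in the PD comparison that leads to the Stage II dose.

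The antibody rule has a similar fault. The endpoint needs a Day-50 result, but under neither reading does the rule simply require one.

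**Working it through.** **Plan's own figures.** The plan gives no calculation for these sets. Its maximum sizes, which bound the groups, do reproduce: 7 × 6 + 6 + 6 = 54 for Stage I, and 54 + 6 + 6 = 66 overall.

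**Step 1: compare the sampling grids in SAP 8.4.** The PD grid has 15 times, and every one is also a PK time.

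| Group | PK times | PK-only draws (PK times − 15) | Hours |
|---|---|---|---|
| Stage I BCD-131, Mircera | 18 | 3 | 0.5, 2, 8 |
| Aranesp | 20 | 5 | 0.5, 2, 8, 16, 36 |
| Stage II | 21 | 6 | 0.25, 0.5, 1, 2, 4, 8 |

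**Step 2: can a volunteer with 15/15 PD values be removed?**
- *Both conditions needed (literal reading).* Yes, but only by missing three or more PK-only draws, since skipping a shared draw would also cost a PD value. With exactly three missed there is C(3,3) = 1 way for BCD-131 and Mircera, C(5,3) = 10 for Aranesp and C(6,3) = 20 in Stage II. All these draws except the 36 h one fall within the 24 h on-site stay (SAP 3.1), so this is unlikely.
- *Either condition enough.* Yes, by any three lost or spoilt PK tubes: C(18,3) = 816, C(20,3) = 1140 or C(21,3) = 1330 combinations.

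**Step 3: can a volunteer with few PD values be kept?** Yes, under both readings. A blood count spoilt at an attended visit is neither a lost PK sample nor a skipped time point. Missed visits are not the problem: three of them lose three PK samples and skip three time points, so the rule applies either way.

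**Step 4: what one wrongful exclusion costs.** The 95% CI half-width of a mean, in SD units, is t(0.975, n−1)/√n.
- n = 3: 4.303/√3 = 2.48. n = 2: 12.706/√2 = 8.98. Ratio 3.6.
- n = 6: 2.571/√6 = 1.05. n = 5: 2.776/√5 = 1.24. Ratio 1.18.

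**Step 5: frequency (assumption only).** The documents give no loss rate. If either condition is enough and each PK tube is lost independently with probability 1%, 2% or 5%, the binomial chance of three or more losses per volunteer is 0.07–0.12%, 0.5–0.8% or 5.8–8.5% across the three grids. For three or more of 15 blood counts spoilt at the same rates, it is 0.04%, 0.3% or 3.6%.

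**Step 6: effect of keeping a volunteer with lost counts (assumed curves).** Take a linear rise to a peak at 168 or 216 h and a linear return to baseline by 504 or 672 h. With three of the 14 post-dose counts missing, AC-Emax is understated by 26–42% in the worst case. Only losses that include the peak matter: C(13,2) = 78 of C(14,3) = 364 triples, or 21%. Averaged over all 364 triples, the understatement is 2.5–4.9%. With two counts missing, the worst case is still 22–29%.

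**Step 7: antibody set.** Read literally, a volunteer with a Day-1 sample and no Day-50 sample stays in the set. If the sponsor meant that either missing sample excludes, a volunteer with a valid Day-50 result and no Day-1 sample is lost. For scale, with one positive and one volunteer without a Day-50 result, the incidence is 1/2 on evaluable samples against 1/3 on set members in a cohort of three, and 1/5 against 1/6 in a group of six.

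**The case against.** **The rule will rarely bite.** Under the literal reading, wrongful exclusion needs several skipped draws, nearly all of them while the volunteer is on site. The larger frequencies need the looser reading and an assumed loss rate. This stands, and it limits the severity.

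**Loss of significance would not settle the dose.** A reader might infer that dropping one of three volunteers removes any chance of a significant result and so changes the dose. SAP 8.2 does say "The statistical analysis will include two-tailed hypothesis testing; the chosen significance level is 0.05", and the smallest exact two-sided Mann-Whitney p moves from 2/C(9,3) = 0.024 (3 vs 6) to 2/C(8,2) = 0.071 (2 vs 6). But SAP 8.2 also applies a Benjamini-Yekutieli correction without defining the family. The best case for 3 vs 6 is 0.0238 × Σ(1/i): 0.0496 for four comparisons, 0.054 for five, 0.062 for seven and 0.077 for fourteen (seven cohorts against two comparators). Beyond four comparisons the exclusion changes nothing on this count. SAP 3.1 also names no significance test for choosing the dose. The inference is not supported; the loss of precision is.

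**A missing Day-50 result is not scored negative.** A reader might infer from the antibody rule that it is. The documents do not say so. Section 7 defines membership of a set, not the denominator, and SAP 8.3 rules out filling in missing data. What remains is an unclear denominator.

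**Existing safeguards.** SAP 8.3 provides for data queries, outlier review and a report of how missing data were handled. None of these sets a completeness limit for PD values or overrides the rule in section 7.

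**A count limit does not protect the peak.** This is correct (step 6) and is taken into the fix.

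**Conclusion.** The PD set rule is wrong as written; the severity is minor. This rests on the text alone: the rule counts PK samples, the PD endpoints use reticulocyte and Hb values at 15 times, and nothing else in either document limits missing PD values. Retention despite spoilt counts holds under both readings of the rule. Wrongful exclusion is unlikely under the literal reading and easier under the other.

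The firm size is the loss of precision: from three volunteers to two, the CI half-width is 3.6 times as wide for a given SD. The loss rates and the response curves are assumptions, given for scale only. The 26–42% understatement of AC-Emax is a worst case and should not be read as typical.

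For immunogenicity, the conclusion is that the set rule does not fit the Day-50 endpoint under either reading. It is not that the incidence will be biased.

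**What to change.** - **PD set.** Define it by PD data, separately for reticulocytes and Hb: dosed, pre-dose value present, and no more than a prespecified number of the 15 PD times missing, regardless of PK tubes. The number is the sponsor's choice.
- **AC-Emax.** Flag the value when counts around the expected peak are missing, since a count limit alone does not guard against this.
- **Day-50 antibody incidence.** Use volunteers with an evaluable Day-50 sample as the denominator, report how many were not evaluable, and flag those without a Day-1 sample, for whom pre-existing binding cannot be ruled out.
- **Protocol.** Align the PD and immunogenicity paragraphs of the synopsis.

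**Cost.** Wording only; no visit or sample is added. A volunteer with many missing blood counts, kept under the present rule, would leave the PD set, which in a cohort of three is a third of the cohort. The antibody denominator may be slightly smaller.
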